4.5.1.3 Summary of genetic assessments and analysis

The purpose of the genetic research is to generate data for use in future retrospective analyses. Future analyses will explore genetic factors that may influence the disposition, efficacy, safety and tolerability to AZD6140 in this protocol. The results of the genetic research will not form part of the clinical study report for this study. The results may be pooled with genetic data from other studies on AZD6140 to generate hypotheses to be tested in future studies.

4.6 Volume of blood sampling

The total volume of blood that will be drawn from each volunteer in this study is as follows:

Table 5 Volume of blood to be drawn from each volunteer

Assessment		Sample volume (mL)	Samples (n)	Total volume (mL)
AZD6140 PK Samples		4	44	176
Blood discarded from indwelling catheter for PK samples		1	44	44
Blood Samples for Genotyping		10	1	10
Safety	Clinical chemistry & Pregnancy	8.5	6	51
	Haematology	4	6	24
	PT, aPTT*	4.5	1	4.5
	Virology Screen	8.5	1	8.5
Total				318

*PT, aPTT will be done at screening only per CPU procedures. Results will not be recorded in the CRF.

4.7 Adverse Events

The methods for collecting adverse events are described below.

4.7.1 Adverse Events

4.7.1.1 Definitions

The definitions of adverse events (AEs), serious adverse events (SAEs) and other significant adverse events (OAEs) are given below. It is of the utmost importance that all staff involved in the study is familiar with the content of this section. The principal investigator is responsible for ensuring this.

Adverse event

An adverse event is the development of an undesirable medical condition or the deterioration of a pre-existing medical condition following or during exposure to a pharmaceutical product, whether or not considered causally related to the product. An undesirable medical condition can be symptoms (e.g., nausea, chest pain), signs (e.g., tachycardia, enlarged liver) or the abnormal results of an investigation (e.g., laboratory findings, ECG). In clinical studies, an AE can include an undesirable medical condition

occurring at any time, including run-in or washout periods, even if no study treatment has been administered.

Serious adverse event

A serious adverse event is an AE occurring during any study phase (i.e., run-in, treatment, washout, follow-up), and at any dose of the investigational product, comparator or placebo, that fulfils one or more of the following criteria:

- Results in death
- Is immediately life-threatening
- Requires in-patient hospitalization or prolongation of existing hospitalization
- Results in persistent or significant disability or incapacity
- Is a congenital abnormality or birth defect
- Is an important medical event that may jeopardise the volunteer or may require medical intervention to prevent one of the outcomes listed above.

The causality of SAEs (i.e., their relationship to study treatment) will be assessed by the investigator(s), who in completing the relevant case report form (CRF) must answer “yes” or “no” to the question “Do you consider that there is a reasonable possibility that the event may have been caused by any of the following – study medication – other medication?” For further guidance on the definition of a SAE and a guide to the interpretation of the causality question, see Appendix B to the Clinical Pharmacology Study Protocol.

Note that SAEs that could be associated with any study procedure should also be reported. For such events the causal relationship is implied as “yes”.

Other Significant Adverse Events (OAE)

OAEs will be identified by the Study Delivery Team Physician in consultation with the appropriate Global Drug Safety Physician during the evaluation of safety data for the Clinical Study Report. Significant adverse events of particular clinical importance, other than SAEs and those AEs leading to discontinuation of the volunteer from study treatment, will be classified as OAEs. Examples of these are marked haematological and other laboratory abnormalities, and certain events that lead to intervention (other than those already classified as serious), dose reduction or significant additional treatment. For each OAE, a narrative may be written and included in the Clinical Study Report.

4.7.1.2 Recording of adverse events

Adverse events will be collected from the point of dosing (Study Period 1, Day 1) through completion of the follow-up visit (visit 4). Serious adverse events will be collected from

the time the informed consent is signed at screening (visit 1) through completion of the follow-up visit (visit 4).

The volunteer will be told to report any AE occurring during the study to the investigator or his personnel. Open standardized AE questioning, such as “Have you had any health problems since the previous visit?” will be done by the investigators or their personnel at each contact with the volunteer. The AE open standardized questioning should be done discreetly in order to prevent the volunteer from influencing each other.

Any AEs observed or reported by a volunteer and/or staff, will be recorded in the CRF. Any AE including clinical findings not resolved at the follow-up visit, will be followed up at an additional visit or telephone contact within 7 days after the follow-up visit or until resolved or explained.

Laboratory and vital sign abnormalities will not be recorded as an AE unless any criterion for an SAE is fulfilled, the volunteer discontinues the study due to the result(s), or the investigator insists that it should be reported as an AE. If a laboratory value or vital sign is associated with clinical signs and symptoms, the signs and symptoms should be reported as an AE and the associated laboratory or vital signs should be considered additional information. Any sign or symptom that fulfils the SAE definition (Appendix B) or is the reason for discontinuation of treatment of investigational products should be reported accordingly.

The following variables will be recorded for each AE noted:

- Onset, resolution
- Intensity (mild/moderate/severe)
- Action(s) taken
- Outcome of the AE
- Causality of the AE (yes or no)
- Whether it constitutes an SAE or not

The intensity rating is defined as:

1. Mild (awareness of sign or symptom, but easily tolerated)
2. Moderate (discomfort sufficient to cause interference with normal activities)
3. Severe (incapacitating, with inability to perform normal activities)

It is important to distinguish between serious and severe AEs. Severity is a measure of intensity whereas seriousness is defined by the criteria in Section 4.7.1.1. An AE of severe

intensity need not necessarily be considered serious. For example, nausea that persists for several hours may be considered severe nausea, but not a SAE. On the other hand, a stroke that results in only a limited degree of disability may be considered a mild stroke but would be a SAE.

Should an overdose (accidental or deliberate) occur it must be reported in accordance with the procedures described in Section 8.3, regardless of whether the overdose was associated with any symptoms or not. All symptoms associated with the overdose should be reported as AEs.

Should a pregnancy occur, it must be reported in accordance with the procedures described in Section 8.4. Pregnancy in itself is not regarded as an AE unless there is a suspicion that an investigational product may have interfered with the effectiveness of a contraceptive medication.

4.7.1.3 Reporting of serious adverse events

Investigators and other site personnel must inform appropriate AstraZeneca representatives of any SAE that occurs in the course of the study within 1 day (i.e., immediately but no later than the end of the next business day) of when he or she becomes aware of it.

The AstraZeneca representative will work with the investigator to compile all the necessary information and ensure that the appropriate AstraZeneca Drug Safety Department receives a report by day one for all fatal and life-threatening cases and by day five for all other SAEs.

Follow-up information on SAEs must also be reported by the investigator within the same time frames.

If a non-serious AE becomes serious, this and other relevant follow-up information must also be provided to AstraZeneca within 1 day as described above. For a non-serious AE that become serious but which is not fatal or life threatening a report should be received within 5 days.

All SAEs have to be reported, whether or not considered causally related to the investigational product or to the study procedure(s). All SAEs will be recorded in the CRF. The investigator and/or Sponsor are responsible for informing the Ethics Committee and/or the Regulatory Authority of the SAE as per local requirements.

5. STUDY MANAGEMENT

5.1 Monitoring

5.1.1 Study monitoring

The monitoring of this study will be performed in accordance with the principles of Good Clinical Practice (GCP) as laid out in the International Conference on Harmonization (ICH) document “Good Clinical Practice: Consolidated Guideline”.

The specific requirements of the genetic part of the study will be discussed with the investigator(s) and other personnel involved with the study.

5.1.2 Data verification

It is a prerequisite of this study that the study monitor has direct access to source data for data verification. This will be done by comparing data from the CRFs with those in the volunteer’s medical notes (permission from the volunteer will be sought as part of the consent process). Such verification is an essential element of quality control, as it allows the rectification of transcription errors and omissions.

Monitoring including source data verification should routinely be performed prior to the transfer of data to Data Management.

Source verification of the genetic consent of participating volunteers will be performed and make sure that the investigational team is adhering to the specific requirements of the genetics aspects of the study.

5.2 Audits and inspections

Authorized representatives of AstraZeneca, a regulatory authority, an Ethics Committee may visit the centre to perform audits or inspections, including source data verification. The purpose of an AstraZeneca audit or inspection is to systematically and independently examine all study-related activities and documents to determine whether these activities were conducted, and data were recorded, analyzed, and accurately reported according to the protocol, GCP guidelines of the ICH and any applicable regulatory requirements. The investigator should contact AstraZeneca immediately if contacted by a regulatory agency about an inspection at his or her centre.

5.3 Training of staff

The principal investigator will maintain a record of all individuals involved in the study (medical, nursing and other staff). He or she will ensure that appropriate training relevant to the study is given to all of these staff, and that any new information of relevance to the performance of this study is forwarded to the staff involved.

Before the first volunteer is entered into the study the investigational staff will have an opportunity to discuss the procedures associated with the collection of blood samples,

extraction of DNA and genetic testing with AstraZeneca personnel. The ethical considerations specific to genotyping and the importance of the informed consent process will be made clear. The requirements for the collections of the volunteer' samples will also be made clear.

5.4 Changes to the protocol

Study procedures will not be changed without the mutual agreement of the principal investigator and AstraZeneca.

If it is necessary for the study protocol to be amended, the amendment and/or a new version of the study protocol must be notified to or approved by each Ethics Committee, and in many countries also the local regulatory authority, before implementation. Local requirements must be followed.

If a protocol amendment requires a change to a particular centre's Master Informed Consent Form, then AstraZeneca and the centre's IEC or IRB must be notified. Approval of the revised Master Informed Consent Form by AstraZeneca and by the IEC or IRB is required before the revised form is used.

AstraZeneca will distribute amendments and new versions of the protocol to each principal investigator(s) who in turn is responsible for the distribution of these documents to his or her Ethics Committee, and to the staff at his or her centre. The distribution of these documents to the regulatory authority will be handled according to local practice.

5.5 Study agreements

The principal investigator at each centre must comply with all the terms, conditions, and obligations of the study agreement for this study. In the event of any inconsistency between this protocol and the study agreement, this protocol shall prevail.

Specific reference to genetics should be included in the agreement. The contractual obligations should not include any additional payment for collecting the samples, unless special processing is required.

5.6 Study timetable and end of study

The study is expected to start in _____ and to be completed in _____.

End of study is defined as data base lock, which is the time point after no volunteer will be exposed to study related activities.

5.7 Data management

5.7.1 Case report forms

Paper CRFs (pCRFs) will be used to record all data not captured electronically. The forms will be in triplicate on carbonless paper. Data should be recorded directly and legibly from

the source documents onto the pCRFs in black ballpoint pen. Corrections to the pCRFs should be made legibly, initialled, and dated. Correction fluid or covering labels must not be used. The top and middle sheets will be collected and forwarded to data management personnel. The bottom sheet will be retained in the Investigator Study File

The AstraZeneca Monitor will check data at the monitoring visits to the investigational site. The Investigator, together with the AstraZeneca Monitor, will ensure that the data in the pCRFs are accurate, complete and legible.

QDS Data Management will enter the pCRF data on an ongoing basis into their standard commercial database. The data will be verified and cleaned with electronic data checks comprised of validated computer programs and manual data review. Any missing, impossible or inconsistent recordings in the pCRFs will be referred back to the Investigator using a data clarification form (DCF) by QDS via AstraZeneca R&D Wilmington, and be documented for each individual volunteer before Clean File Data status is declared. Responses should be received by QDS Data Management and updated within an agreed number of days upon generating the data queries. These timelines will be reduced nearing Clean File. Clean File will be declared when all of the following have been completed: all data discrepancies are resolved or accepted; all SAEs have been reconciled with the clinical database; all coding is complete and has been medically reviewed and approved; and quality control of the database against the pCRF and relevant data sources has been completed.

5.7.2 Electronic data capture at bedside

During the study days, data will be captured electronically at bedside using Initiator PRO.

The Investigator will ensure that the captured data are correct before exported from the Initiator PRO data capture system. Any changes made during validation will be documented with a full audit trail within the Electronic Data Capture application.

Any missing, impossible or inconsistent entries discovered after the data have been exported from the Initiator PRO data capture system will be referred back to the Investigator using data query forms, and be documented for each individual volunteer before clean file status is declared.

5.7.3 Genetic data

In the case of genotypic data, only the date the volunteer gave consent to participation in the genetic research and the date the blood sample was taken from the volunteer will be recorded in the CRF and database.

The genotypic data generated from the study will be stored in the AstraZeneca Laboratory Information Management System (LIMS) database or other appropriate system. This database is a secure database, which is separate from the database used for the main study. Some or all of the datasets from the main study may be duplicated within the AstraZeneca LIMS database for exploratory genetic analysis.

5.8 Reporting of genotypic results

Results from any genetic research performed will be reported separately from the clinical study report. AstraZeneca will not provide individual genotype results to volunteers, their family members, any insurance company, an employer, clinical study investigator, general physician or any other third party, unless required to do so by law. The volunteer's DNA will not be used for any purpose other than those described in the study protocol.

Individual volunteers will not be identified in any report or publication resulting from this work. The data and results of this study may be reviewed with collaborators and published, but neither the volunteer's name nor any other personal identifiers will appear in any publication or report.

6. PHARMACOKINETIC, PHARMACODYNAMIC, SAFETY, GENETIC AND STATISTICAL METHODOLOGY

6.1 Pharmacokinetic / pharmacodynamic evaluation

6.1.1 Calculation or derivation of pharmacokinetic variables

The pharmacokinetic analyses will be performed by Clinical Pharmacokinetics, Clinical Pharmacology, AstraZeneca, Wilmington, DE USA.

Plasma concentrations of AZD6140 and its metabolite ARC124910XX will be listed and depicted graphically as a function of time after single oral and intravenous doses.

PK parameters- 1) C_{max} , t_{max} , $t_{1/2}$, $AUC_{(0-t)}$ and AUC for AZD6140 and AR-C124910XX after intravenous and oral doses; 2) $AUMC$, MRT (IV) for AZD6140 and AR-C124910XX; and CL , V_{ss} , and V_z for AZD6140 after intravenous dosing and 3) $AUMC$, MRT oral and MAT after oral dosing for AZD6140 and AR-C124910XX, as well as CL/F for AZD6140 after oral dosing; will be estimated using non-compartmental analysis. Metabolite: parent C_{max} and AUC ratios will be calculated following IV and oral dosing. C_{max} will be estimated as the highest measured concentration and t_{max} is the time to maximum concentration after single dose administration. The terminal elimination rate constant (λ_z) will be calculated by log-linear regression of the terminal portion of the plasma concentration-time profile. The terminal elimination half-life ($t_{1/2}$) will be calculated as $0.693/\lambda_z$. AUC and $AUMC$ will be calculated using the linear trapezoidal method up to the last measurable concentration (AUC_{0-t}) and thereafter by extrapolation of the terminal elimination phase to infinity. AZD6140 CL and CL/F will be estimated as the ratio of AZD6140 dose and AUC after intravenous and oral doses, respectively. Mean residence time (MRT) will be calculated as the ratio of $AUMC$ to AUC with a correction for non-instantaneous infusion input following intravenous administration. Mean absorption time (MAT) will be estimated as the difference between MRT oral and MRT IV. Steady state volume of distribution (V_{ss}) will be estimated as the product of CL and MRT iv, and terminal phase volume of distribution, V_z , will be estimated as the ratio of CL to λ_z .

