The duration of healthy volunteer participation will be approximately 53 days, including:

- **Screening period (visit 1):** within 28 days before Study Period 1, Day 1.
- **Study Period 1 (visit 2):** will consist of admission to the clinical research centre on Day -1, administration of study medication according to randomisation schedule at Day 1, and continued inpatient stay until after the 72 hour post-dose blood collection is performed and all safety assessments are complete.
- **Washout Period:** at least 7 days between discharge from Study Period 1 and dosing of Study Period 2.
- **Study Period 2 (visit 3):** will consist of admission to the clinical research centre on Day -1, administration of study medication according to randomisation schedule at Day 1, and continued inpatient stay until after the 72 hour post-dose blood collection is performed and all safety assessments are complete.
- **Follow-up visit (visit 4):** within 3-5 days of the last inpatient day of Study Period 2.

Variables

- Pharmacokinetic

Treatment A (Oral administration): Blood samples for the pharmacokinetic assessment of AZD6140 and its metabolite AR-C124910XX will be obtained starting on Day 1 of Study Period 1 and Study Period 2 at the following time points:

- Pre-dose, 15min, 30min, 1, 1.5, 2, 2.5, 3, 4, 5, 6, 8, 10, 12, 16, 20, 24, 36, 48, and 72 hours post-dose.

Treatment B (Intravenous administration): Blood samples for the pharmacokinetic assessment of AZD6140 and its metabolite AR-C124910XX will be obtained starting on Day 1 of Study Period 1 and Study Period 2 at the following time points:

- Pre-dose, 15min, 30min, 40min, 50min, 1, 1.25, 1.5, 1.75, 2, 2.5, 3, 4, 5, 6, 8, 10, 12, 16, 20, 24, 36, 48, and 72 hours post dose.

Pharmacokinetics will be assessed by: absolute bioavailability (F), single dose C_{max} , t_{max} , AUMC, $AUC_{(0-t)}$, AUC, and $t_{1/2}$ of AZD6140 and AR-C124910XX, metabolite to parent C_{max} and AUC ratios, CL (IV only), CL/F (oral), V_z and V_{ss} (IV only), MAT (oral), and MRT of AZD6140 only.

- **Pharmacodynamic**

Not applicable.

- **Safety**

Safety and tolerability will be assessed by the incidence and severity of adverse events, vital signs, clinical laboratory parameters, physical examination, and electrocardiograms.

- **Genetics**

Genetic analysis of the genes that are involved in the absorption and disposition, and the response to AZD6140 including adverse effects may be performed.

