1.2 Rationale

The purpose of this study is to help complete the pharmacokinetic characterization of AZD6140. AZD6140 is extensively metabolized by CYP3A and other enzymes, and is a substrate of P-glycoprotein, an efflux transporter located in the gastrointestinal tract and the liver. The absolute bioavailability of orally administered AZD6140 (an estimate of the fraction of the dose that reaches the systemic circulation intact or escapes the “first pass effect”) is not currently known. The minimal extent of absorption is at least 27% based on the urinary recovery of total radioactivity following oral administration of a ¹⁴C-AZD6140 dose. Use of the intravenous dose in this study will allow the estimation of the absolute bioavailability (F) following oral dosing, the total body or systemic clearance (CL) and the volume of distribution (V_{ss}) of AZD6140.

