6.4.2.2 Secondary objectives

Characterization of the pharmacokinetics of AZD6140 following oral and intravenous administration of AZD6140 will be based on single dose C_{max} , t_{max} , $AUC_{(0-t)}$, AUC, $t_{1/2}$, and CL/F of AZD6140.

Characterization of the pharmacokinetics of AR-C124910XX following oral and intravenous administration of AZD6140 will be based on single dose C_{max} , t_{max} , $AUC_{(0-t)}$, AUC, $t_{1/2}$ of AR-C124910XX; and AR-C124910XX:AZD6140 C_{max} and AUC ratios.

Characterization of the pharmacokinetics of AZD6140 and AR-C124910XX after oral administration of AZD6140 will be based on single dose AUMC, MRT oral and MAT and CL/F for AZD6140.

Characterization of the pharmacokinetics of AZD6140 and AR-C124910XX after intravenous administration of AZD6140 will be based on single dose AUMC, MRT (IV) and CL, V_{ss} , and V_z for AZD6140. The safety and tolerability of AZD6140 will be examined by collection of adverse events, vital signs, and clinical laboratories.

The examination of the safety and tolerability of AZD6140 will be conducted based on AE, clinical lab, vital sign and ECG data.

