6.4.4.1 Pharmacokinetics

Only data from volunteers in the PK analysis set will be summarized and formally analyzed. All PK and plasma concentration data will be listed. Any data excluded from the analysis will be flagged accordingly.

The absolute bioavailability (F), where $F = (AUC(oral)/Dose(oral))/(AUC(IV)/Dose(IV))$, of AZD6140 following oral and intravenous administration will be analyzed as follows: Dose-normalized AUC values for the two formulations of AZD6140 will logarithmically transformed. An ANOVA model will then be fit using these log-scale values. The effect of formulation will be the primary contrast [$\log(AUC(oral)/Dose(oral)) - \log(AUC(IV)/Dose(IV))$]. The effect of formulation will be estimated using the $1s_{mean}$ and its 95% confidence interval. The $1s_{mean}$ and 95% confidence interval will then be exponentiated in order to estimate the absolute bioavailability. The $1s_{means}$ and 95% confidence intervals will also be calculated and exponentiated for each treatment formulation

PK parameters and plasma concentration data for each moiety (AZD6140, AR-C124910XX) will be summarized using descriptive statistics by AZD6140 formulation. Descriptive statistics will also include geometric mean and CV for all parameters except t_{max} , which will be summarized using only N, minimum, median and maximum. Geometric mean and individual plasma concentration-time profiles will be presented by AZD6140 formulation. AUC and C_{max} for each moiety will also be presented graphically as a function of AZD6140 formulation.

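### Section 6.1.1 derives MRT and MAT for the metabolite, contradicting the synopsis; the metabolite's route difference is an absorption time only if none of it forms pre-systemically

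*Protocol*

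**What the plan says.** The protocol lists the residence-time parameters in three places.

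- **Synopsis, Variables (Pharmacokinetic).** AUMC is listed for both analytes, but the list closes with "MAT (oral), and MRT of AZD6140 only".
- **Section 6.1.1.** It plans "MRT (IV) for AZD6140 and AR-C124910XX" and then "MRT oral and MAT after oral dosing for AZD6140 and AR-C124910XX". The same sentence assigns CL, Vss, Vz and CL/F to AZD6140 alone, so it distinguishes the analytes parameter by parameter.
- **Section 6.4.2.2.** The list for the metabolite's own characterisation contains neither MRT nor MAT. The next sentence, on oral dosing, opens with both analytes and says that their characterisation "will be based on single dose AUMC, MRT oral and MAT and CL/F for AZD6140". The closing words may govern the whole list or CL/F only. The sentence on intravenous dosing has the same structure.

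Section 6.1.1 gives one definition of each quantity, with no exception for the metabolite. MRT is the "ratio of $AUMC$ to AUC with a correction for non-instantaneous infusion input" after the intravenous dose, and "Mean absorption time (MAT) will be estimated as the difference between MRT oral and MRT IV".

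On summaries, section 6.4.4.1 states: "Descriptive statistics will also include geometric mean and CV for all parameters except" tmax. MAT is not exempted.

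**The concern.** The two parameter lists are incompatible, and both serve a secondary objective, so whoever programs the analysis has to choose between them.

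The choice matters because subtracting MRTs between routes isolates the absorption step only when everything after absorption is the same by both routes. That is true for the parent. It is not true for a metabolite if some of it is formed during absorption, because that fraction never waits through the parent's residence time. Section 1.2 says that "AZD6140 is extensively metabolized by CYP3A and other enzymes", so pre-systemic formation cannot be ruled out in advance. Following 6.1.1, the study report could then carry a metabolite mean absorption time that is not one, possibly with a negative value, and a metabolite MRT that also contains the parent's residence time.

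**Working it through.** The protocol states no figure on this point, so there is none to reproduce. The check is algebra, followed by an illustration.

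**Inputs from the protocol**
- Parent half-life: about 11 h (section 1.1).
- Infusion: 150 mL at 300 mL/h, that is 150/300 = 0.5 h, so the correction to the intravenous MRT is 0.5/2 = 0.25 h (section 3.4.2).
- Absolute bioavailability: stated to be unknown (section 1.2).

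**Assumed, because the protocol does not give them**
- phi, the share of oral metabolite AUC formed pre-systemically.
- MAT, the parent's true mean absorption time.
- MRT(parent). A one-compartment reading of the half-life gives 11/ln 2 = 15.9 h; multi-phasic disposition would give less, so 8 h is shown as well.

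**Derivation (linear kinetics)**
1. Metabolite after intravenous parent, infusion-corrected: AUMC/AUC = MRT(parent) + MRT(metabolite).
2. Metabolite after oral parent:
   - the share phi takes MAT + MRT(metabolite);
   - the share 1 - phi takes MAT + MRT(parent) + MRT(metabolite);
   - the weighted mean is MAT + (1 - phi) x MRT(parent) + MRT(metabolite).
3. Oral minus intravenous, the protocol's MAT rule applied to the metabolite: MAT - phi x MRT(parent).
4. The same rule applied to the parent: [MAT + MRT(parent)] - MRT(parent) = MAT, whatever the first-pass extent.

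So the metabolite difference equals MAT only at phi = 0, and it is negative when phi > MAT/MRT(parent). Step 1 also shows that the metabolite's intravenous MRT is not its own residence time, whatever phi is.

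**Value of phi at which the sign changes, MAT/MRT(parent)**

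| MRT(parent) | MAT 1 h | MAT 2 h | MAT 4 h |
|---|---|---|---|
| 15.9 h | 0.06 | 0.13 | 0.25 |
| 8 h | 0.125 | 0.25 | 0.50 |

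**Metabolite difference at MRT(parent) = 15.9 h and true MAT = 2 h**

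| phi | 0 | 0.1 | 0.2 | 0.4 |
|---|---|---|---|---|
| Result (h) | 2.00 | 0.41 | -1.17 | -4.35 |

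Numerical integration of a one-compartment parent and metabolite model, with the 0.5 h infusion and 0.25 h correction, agreed with the formula to 0.01 h. In that model the parent difference returned 1.00, 2.00 and 4.00 h for true MATs of 1, 2 and 4 h, with first-pass fractions from 0 to 0.6.

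**Link to data the trial will collect.** Under the same linearity, phi = 1 - R(IV)/R(oral), where R is the metabolite-to-parent AUC ratio already planned for both routes. The threshold of 0.13 (unrounded 2/15.87 = 0.126) corresponds to R(oral)/R(IV) = 1/(1 - 0.126) = 1.14, an oral ratio about 14% above the intravenous one.

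**The case against.** The strongest reply is that little depends on this. The parameters are descriptive and carry no hypothesis or decision rule. F, its ANOVA, CL and Vss use parent data only. MRT is defined openly as AUMC/AUC, so a reader can see what was computed, and for the metabolite's MRT the complaint is mainly one of naming. All of this stands and limits the weight of the point. It does not remove the conflict between the two lists, nor does it make the metabolite's route difference an absorption time.

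Three stronger readings are tempting and are not supported.

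- **A reader might infer that the metabolite MAT will usually be negative.** The sign depends on phi, MAT and MRT(parent), none of which is given. Over an assumed uniform spread of MAT from 0.5 to 4 h and MRT(parent) from 6 to 15.9 h, about 5% of cases are negative for phi between 0 and 0.1, 33% for 0.1 to 0.2, 74% for 0.2 to 0.4 and 98% for 0.4 to 0.7. The answer depends almost entirely on a quantity that the protocol does not supply.
- **A reader might infer that the protocol reports first-pass formation of the metabolite.** Section 1.2 mentions the first-pass effect only when explaining what absolute bioavailability means, and says that bioavailability is unknown. Extensive metabolism makes phi above zero plausible; it does not quantify it.
- **A reader might infer that the parent's MAT cannot be summarised as planned.** A difference can be zero or negative, and one such value leaves the geometric mean undefined. The chance of at least one in 10 volunteers, taking the difference as normal with SD = sqrt(2) x CV x 11.8 h, runs from 3% (MAT 2.25 h, CV 5%) to 99% (MAT 1.25 h, CV 20%). Every one of those inputs is assumed. Section 6.4.4 already prescribes N, mean, SD, minimum, median and maximum by default, so only the added geometric mean would fail.

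**Conclusion.** The point holds. Section 6.1.1 contradicts the synopsis on which analytes receive MRT and MAT, and 6.4.2.2 does not settle it. Given linear kinetics, the rule in 6.1.1 yields a wrongly named metabolite parameter whenever any metabolite forms pre-systemically. The error is phi x MRT(parent): at most about 1.6 h for each 0.1 of phi if MRT(parent) is 15.9 h, and 0.8 h if it is 8 h. Whether the reported value would be negative, and how often, cannot be determined from the protocol. The consequence is confined to secondary descriptive results, so the text should be corrected, but nothing in the primary analysis depends on it. The geometric mean of MAT is a minor side issue.

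**What to change.** - **Sections 6.1.1 and 6.4.2.2:** align with the synopsis by deriving MRT and MAT for AZD6140 only, and reword 6.4.2.2 so that the analyte for each parameter is unambiguous. AUMC for the metabolite can stay, since the synopsis includes it.
- **If the metabolite's AUMC/AUC is wanted:** report it by route as a mean transit time, and do not report the route difference as MAT.
- **Section 6.4.4.1 (minor):** exempt MAT from the geometric mean, alongside tmax, and rely on the default statistics in 6.4.4.

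The cost is wording in three sections and a few fewer derived parameters. Sampling, assays, the primary analysis and the number of volunteers do not change.
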